#### STUDY DESIGN

This is a two-group, active-control, RCT of the KIU! an online intervention. Participants will be randomized to two groups in equal proportions (KIU! condition n=450; control arm n=450). The KIU! intervention involves 7 modules completed across three sessions, done at least 24 hours apart (i.e., at least 3 days), and totaling ~2 hours to content. Across these modules, the KIU! intervention uses diverse delivery methods (e.g., videos, animation, games) to address HIV knowledge, motivate safer behaviors, teach behavioral skills, and instill self-efficacy for preventive behaviors. The control condition contains the same number of modules as the KIU! condition, with the same requirement to participate across three sessions. It reflects HIV information that is currently available on many websites so as to understand how the KIU! intervention improves upon what is currently available online. Booster sessions will be delivered at 3 and 6 months for each arm.

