B.12. Power and Sample Size. All power calculations were performed in R version 2.14.0 and using common sample size formula for repeated measures with nominal Type I error rates (i.e.  $\alpha$ =.05) and effect estimates based on our preliminary studies. We will screen approximately 4500 YMSM, enroll 900 YMSM, and assume 80% retention based on our preliminary studies. Assuming participants are randomized to two groups in equal proportions, we will have 97% power to detect a 11% reduction in the rate of unprotected sex (ERR = 0.89) due to the intervention, assuming the correlation between repeated measures is 0.8. The correlation among repeated measures plays an important role in the calculation; in this case, our power calculation is conservative if the correlation among repeated measures is, in fact, weaker than 0.8. The smallest effect size with which we will have 80% power to detect is a 6.5% reduction in the rate of unprotected sex. Technically speaking, our study will have greater power than what is reported here after we adjust for our blocked design. In conclusion, we will have 80% power to detect an effect size equal to half of what we observed in our pilot trial and less than half of the lower bound of effect sizes seen in other HIV prevention programs with MSM. For our primary biomedical endpoint of STI incidence, we assume the annual incidence based on our longitudinal cohort studies in the range of 10 to 15%. If the incidence rate in the control group is 10%, we will have 81%, 70%, and 56% power to detect an incidence reduction of 7%, 6%, and 5%, respectively. If the incidence rate in the control group is higher, say 15%, then the power reduces to 71%, 60%, and 47%, respectively. The objective of aim 3 is to estimate the intervention effect among subgroups and test for significant differences. In data analyses, this will be achieved by testing 2-way interactions, treatment by subgroup. For a conservative power calculation, we repeated the power calculations as per aim 1 with a reduced sample size. Assuming N=200 per group (say, for racial/ethnic subgroups), an ERR=0.89 as above, and strong correlation among repeated measures (i.e. 0.8), we will have 91%, 85%, and 77% power to detect a 10%, 9%, and 8% reduction in the rate of unprotected sex among YMSM, respectively, due to KIU! intervention. The power will be less for effect sizes more subtle than 8% and less for smaller subgroups. In addition to racial/ethnic subgroups, other subgroups of interest include sexual orientation identity groups (81% gay, 17% bisexual identified) and relationship groupings (30% recent serious relationships). The power for each subgroup comparison will be similar to the power described above.

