#### C. HUMAN SUBJECTS

## C.1. RISKS TO HUMAN SUBJECTS

**C.1.a.** Human Subjects Involvement, Characteristics, and Design. We will screen 4532 ethnically diverse 18–29 year-old young men who have sex with men (YMSM) following an HIV negative test result from community clinics in Chicago, New York, and Atlanta or at a university site (Emory and Hunter). (This total sample includes 12 YMSM who will participate in acceptability and usability testing prior to implementation.) About 20% of these young men (n = 900) are anticipated to enroll into and complete the study. Investigators with a history of successfully conducting HIV behavioral research will be supervising research in these cities. Three academic institutions (Northwestern University, Hunter College, and Emory University) with exemplary human subjects protection programs will be involved in participant recruitment. The investigative team has extensive experience conducting research and providing services to YMSM. The Principal Investigator has been a member of the Institutional Review Board (IRB) and has expertise in ethical issues related to conducting research with sexual minority youth.

MSM will range in age from 18-29 years, consistent with findings regarding emerging adulthood as a period of heightened risk for STIs/HIV among MSM. We will recruit a racially and ethnically diverse sample, representing both high-risk YMSM in Chicago, Atlanta, and New York, as well as the demographics of the population seeking services at each recruitment site. As described in the research design, the size and epidemiologic trends of the HIV/AIDS epidemic in each city make them good candidates for conducting an RCT among YMSM. These cities represent distinct geographical regions (i.e. Midwest, Southeast, East Coast) with notable differences in population demographics and culture. This diversity will allow examination of whether the intervention works equally well in a variety of urban settings, thus increasing our ability to draw conclusions about the generalizability of findings. Given site-specific recruitment patterns, we will readily achieve representation across White, Black, and Latino groups, but we will also stratify enrollment to equal 1/3 for each group). Each site will screen approximately 1250 YMSM and enroll approximately 250 YMSM.

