- b) Randomize participants to either the highly interactive and engaging KIU! intervention or an HIV knowledge condition similar to existing web-based HIV educational materials.
- c) Measure intervention outcomes through 12 months post-intervention. The primary behavioral outcome will be the count of unprotected anal sex acts and the primary biomedical outcome will be STI incidence. Additional behavioral outcomes include: alcohol and drug use prior to sex, risky sex after substance use, condom errors, IMB factors, and receipt of an HIV test. We will test for dose effects and decay in intervention effects over time.

Aim 3: Explore if the KIU! intervention has differential efficacy across important sub-groups of YMSM. We will explore moderators of intervention effects by testing for significant differences in the magnitude of intervention effects based on the types of substances used prior to sex, as well as race/ethnicity, relationship status, and gay/bisexual identity. These findings will be used to assist in future targeting of KIU! delivery and identify need for further intervention tailoring.

A2. Study design.

This is a two-group, active-control, RCT of KIU!, an online intervention. Participants will be randomized to two groups in equal proportions (KIU! condition n=375; control arm n=375). The KIU! intervention involves 7 modules completed across three sessions (See Table 1 for module descriptions),done at least 24 hours apart (i.e., at least 3 days), and totaling ~2 hours to content. An innovative aspect of KIU! is that each module is based on a particular setting or situation relevant to the lives of YMSM, with developmentally appropriate health behavior change content embedded within each of these settings. Module content is designed to be

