
Timed Post-Release Testing: We will use time spent on intervention and booster sessions as a proxy for participant engagement and as a means to refine future implementations of KIU!. In order to determine a baseline measurement for the amount of time it takes to complete each intervention and booster session, we will recruit 20 participants via online social media and application ads. We are recruiting participants who meet the same eligibility requirements as the 900 participants who were enrolled into the KIU! intervention. Potential participants will click the ad, fill out a screener, and, if eligible, provide contact information. They will then be contacted by a KIU! study staff who will describe KIU! in greater detail. If they are still interested in participating in the timed post-release testing, a research assistant will email potential participants a link to an online consent form. Once the participant has consented, a research assistant will email them a unique link to the first intervention session. Participants will be given ten days to complete the three intervention sessions and 3- and 6- month booster sessions. After participants complete the 6 month booster session, study staff will call participants to complete a 10 – 15 minute exit interview. Participants will be reminded that the conversation will be recorded, all of the information they provide during the exit interview is confidential, and that they can refuse to answer any questions that they do not feel comfortable answering. The study team will transcribe the audio and review responses for feedback on the intervention. The information gained from the qualitative exit interviews will be used to continue to refine the intervention in future iterations. Overall, participants will spend approximately 2 hours and 45 minutes completing study activities (2 ½ hours for the online intervention and booster sessions, and 10 – 15 minutes for the phone exit interview). Participants must complete the intervention, two booster sessions, and phone exit interview to be mailed a physical \$50 Visa gift card.

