All power calculations were performed in R version 2.14.0 and using common sample size formula for repeated measures²¹⁰ with nominal Type I error rates (i.e. α =.05) and effect estimates based on our preliminary studies. We will screen approximately 4500 YMSM, enroll 900 YMSM, and assume 80% retention based on our preliminary studies. Assuming participants are randomized to two groups in equal proportions (KIU! condition n=375; control arm n=375), we will have 97% power to detect a 11% reduction in the rate of unprotected sex (ERR = 0.89) due to the intervention, assuming the correlation between repeated measures is 0.8. The correlation among repeated measures plays an important role in the calculation; in this case, our power calculation is conservative if the correlation among repeated measures is, in fact, weaker than 0.8. The smallest effect size with which we will have 80% power to detect is a 6.5% reduction in the rate of unprotected sex. Technically speaking, our study will have greater power than what is reported here after we adjust for our blocked design. In conclusion, we will have 80% power to detect an effect size equal to half of what we observed in our pilot trial and less than half of the lower bound of effect sizes seen in other HIV prevention programs with MSM²⁶. For our primary biomedical endpoint of STI incidence, we assume the annual incidence based on our longitudinal cohort studies in the range of 10 to 15%. If the incidence rate in the control group is 10%, we will have 81%, 70%, and 56% power to detect an incidence reduction of 7%, 6%, and 5%, respectively. If the incidence rate in the control group is higher, say 15%, then the power reduces to 71%, 60%, and 47%, respectively. The objective of aim 3 is to estimate the intervention effect among subgroups and test for significant differences. In data analyses, this will be achieved by testing 2-way interactions, treatment by subgroup. For a conservative power calculation, we repeated the power calculations as per aim 1 with a reduced sample size. Assuming N=200 per group (say, for racial/ethnic subgroups), an ERR=0.89 as above, and strong correlation among repeated measures (i.e. 0.8), we will have 91%, 85%, and 77% power to detect a 10%, 9%, and 8% reduction in the rate of unprotected sex among YMSM, respectively, due to KIU! intervention. The power will be less for effect sizes more subtle than 8% and less for smaller subgroups. In addition to racial/ethnic subgroups, other subgroups of interest include sexual orientation identity groups (81%

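### The six STI power figures are not the power for the stated reductions on the stated design, and the SAP's 375 per arm contradicts 900 enrolled and the Protocol's 450 per arm

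*Protocol*

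**What the plan says.** **Power for STI incidence.** Protocol B.12 assumes an annual incidence of 10 to 15% and states "If the incidence rate in the control group is 10%, we will have 81%, 70%, and 56% power to detect an incidence reduction"; the three sizes considered are 7%, 6% and 5%. For a control rate of 15%, SAP A.5 says "then the power reduces to 71%, 60%, and 47%, respectively". The six figures are the same in both documents. The shared inputs are alpha .05, equal allocation and "enroll 900 YMSM, and assume 80% retention based on our preliminary studies". All power calculations are said to use a common formula for repeated measures. A correlation of 0.8 is given for unprotected sex, and none for STI incidence. For the STI endpoint the documents do not state the test, the sidedness, the analysed number, or whether the reductions are percentage points or relative.

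**Sample size per arm.**
- Protocol, Study Design: "Participants will be randomized to two groups in equal proportions (KIU! condition n=450; control arm n=450".
- SAP A2: "Participants will be randomized to two groups in equal proportions (KIU! condition n=375; control arm n=375".
- SAP A.5, in the sentence on unprotected sex: "Assuming participants are randomized to two groups in equal proportions (KIU! condition n=375; control arm n=375". The sentence before it says 900 will be enrolled.
- SAP A.3, Timed Post-Release Testing: "the 900 participants who were enrolled into the KIU! intervention".
- Protocol C.1.a: "Each site will screen approximately 1250 YMSM and enroll approximately 250 YMSM", with three sites and, in the same section, n = 900.

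**The concern.** A power statement should follow from the design printed beside it. Here the power seems low for falls as large as 10% to 3% with several hundred men per arm. The per-arm number needed to check it is also given two ways.

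STI incidence is the primary biomedical endpoint. Readers will use these figures to judge what reduction the trial could detect and how to read a null result. On the percentage-point reading, someone told that power was 56% for a fall from 10% to 5% might excuse a null result as underpowered, when the stated inputs give about 72%.

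**Working it through.** **1. Analysed number.** 900 × 0.80 = 720; 720 / 2 = **360 per arm**.

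**2. Test (an assumption, because none is stated).** Pooled two-proportion z-test, two-sided 0.05, reductions in percentage points:

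power = Φ( (|p1 − p2| − z·√(2·p̄(1 − p̄)/n)) / √((p1(1 − p1) + p2(1 − p2))/n) ), with z = 1.96 and p̄ = (p1 + p2)/2.

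Example, 10% against 5% at n = 360. Here p̄ = 0.075, the null standard error is 0.01963 and the alternative standard error is 0.01954. Then (0.05 − 1.96 × 0.01963)/0.01954 = 0.590, and Φ(0.590) = 72.2%. The documents state 56%.

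**3. All six figures (power, %).**

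| | 10%: −7 | −6 | −5 | 15%: −7 | −6 | −5 |
|---|---|---|---|---|---|---|
| Stated | 81 | 70 | 56 | 71 | 60 | 47 |
| n = 360 | 96.9 | 88.6 | 72.2 | 83.9 | 69.8 | 52.7 |
| Gap at 360 (points) | +15.9 | +18.6 | +16.2 | +12.9 | +9.8 | +5.7 |
| n = 450 | 99.0 | 94.3 | 81.4 | 91.0 | 79.2 | 62.1 |
| n = 375 | 97.4 | 89.8 | 74.0 | 85.3 | 71.6 | 54.4 |
| n = 300 (375 × 0.80) | 93.7 | 82.3 | 64.3 | 76.8 | 61.9 | 45.7 |

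At 450, 375 and 360 no figure is reproduced within 2 points. At 300, two of the six are.

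**4. Other readings at 360 per arm.**
- One-sided (z = 1.645): 98.6/93.6/81.8 and 90.4/79.8/65.0, further from the stated figures.
- Relative reductions of 7/6/5%, two-sided, both tails: 6.2/5.9/5.6 and 6.9/6.4/5.9. One-sided power stays below about 12% at every documented n.
- A repeated-measures variance factor (1 + (m − 1)ρ)/m, taking m = 2 (baseline and 12 months) and borrowing ρ = 0.8. The factor is 0.9, so 360 acts as 360/0.9 = 400. Power for reductions is then 98.1/91.5/76.7 and 87.5/74.3/57.1, again further away.
- Unpooled, continuity-corrected, arcsine, Poisson, log-rate-ratio, Schoenfeld and control-arm-variance formulas were also tried at 450, 375, 360 and 300 per arm. Isolated figures match (for example 47% at 360 with the log rate ratio), but never all six for reductions.

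**5. Do the six figures imply one n?** Solving each for n with the formula in step 2 gives 199, 223, 248, 262, 288 and 311 per arm. On that formula they do not share a sample size.

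**6. Per-arm and per-site counts.** 450 × 2 = 900. 375 × 2 = 750. 250 × 3 = 750, and the 1,250 screened per site gives 3,750 rather than about 4,500. The retained number is 360, so 375 is not 900 after dropout either.

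**The case against.** **The test is the reviewer's choice.** This is fair. The plan names a repeated-measures formula and the planned analysis is a covariate-adjusted mixed model, so a plain two-proportion test is not the sponsor's stated method. It limits any claim about the exact size of the gap. It does not rescue the figures: the repeated-measures factor tried in step 4 raises power further, and none of the other formulas reproduces the set at a documented n.

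**The plan errs on the safe side.** A reader might infer that the documents simply understate STI power by 6 to 19 points. That holds only for percentage points, 360 per arm and a two-sided pooled test. At 300 per arm the gaps run from about +13 to −1, and on a relative scale the stated figures are far too high. The documents do not settle the scale.

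**The cause is obvious.** A reader might infer that the differences were added to the control rate instead of subtracted (10% against 17/16/15%, 15% against 22/21/20%). The pooled formula then fits all six within 1.3 points at 396 per arm two-sided. With the step 4 factor, so at a documented 360 acting as 400, it fits within 1.7. But a one-sided formula using the control-arm variance for both arms fits the reductions within 1.8 points at 244 per arm. Several formulas can therefore mimic the set, and no document shows the run, so a direction error is not established.

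**375 is only a stale number.** Probably so: the SAP says 900 in several other places, and the Protocol, which carries the later date (12/12/16 against 11/9/16), says 450 per arm. The 375 sits in the sentence on unprotected sex, and nothing says it underlies the STI figures. The two defects are separate. The contradiction still stands in current SAP text.

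**Conclusion.** Both parts are wrong as written.

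1. The six STI power figures do not follow from the stated design. This holds for absolute and relative reductions, one- or two-sided, across the formulas tried. The size and sign of the error are conditional: about 6 to 19 points too low on the assumptions in steps 1 and 2, and far too high if the reductions are relative.
2. The SAP's 375 per arm (750) contradicts the SAP's own 900 and the Protocol's 450 per arm. The Protocol's 250 per site shares the 750 total. This part needs no assumption.

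A reader might go on to infer that only 750 were randomized. The documents do not support that, since SAP A.3 refers to 900 as already enrolled. That 375 and 250 are left over from a 750-person design is plausible, but stated nowhere. These are reporting errors on a primary endpoint and on the sample size; they do not touch trial conduct.

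**What to change.** - **Counts.** Correct the per-arm number in SAP A2 and A.5 to agree with 900 (450 per arm). Correct the per-site number in Protocol C.1.a likewise: 900/3 = 300 enrolled, since B.10 plans equal enrollment across cities. Check the 1,250 screened per site against the 4,500 total.
- **STI power.** In Protocol B.12 and SAP A.5, state the two rates compared, the scale, the test, the sidedness, any repeated-measures correlation and the analysed number. Rerun that one calculation and replace all six figures. If it is the two-sided pooled test at 360 per arm in percentage points, expect about 97/89/72% and 84/70/53%; these are an illustration, not values to adopt without the rerun.
- **Optional.** Check whether the original run compared the control rate with a higher rate.

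The cost is one paragraph in each document, two per-arm statements in the SAP and one per-site sentence in the Protocol, plus a short rerun.

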#### C. HUMAN SUBJECTS

## C.1. RISKS TO HUMAN SUBJECTS

**C.1.a.** Human Subjects Involvement, Characteristics, and Design. We will screen 4532 ethnically diverse 18–29 year-old young men who have sex with men (YMSM) following an HIV negative test result from community clinics in Chicago, New York, and Atlanta or at a university site (Emory and Hunter). (This total sample includes 12 YMSM who will participate in acceptability and usability testing prior to implementation.) About 20% of these young men (n = 900) are anticipated to enroll into and complete the study. Investigators with a history of successfully conducting HIV behavioral research will be supervising research in these cities. Three academic institutions (Northwestern University, Hunter College, and Emory University) with exemplary human subjects protection programs will be involved in participant recruitment. The investigative team has extensive experience conducting research and providing services to YMSM. The Principal Investigator has been a member of the Institutional Review Board (IRB) and has expertise in ethical issues related to conducting research with sexual minority youth.

MSM will range in age from 18-29 years, consistent with findings regarding emerging adulthood as a period of heightened risk for STIs/HIV among MSM. We will recruit a racially and ethnically diverse sample, representing both high-risk YMSM in Chicago, Atlanta, and New York, as well as the demographics of the population seeking services at each recruitment site. As described in the research design, the size and epidemiologic trends of the HIV/AIDS epidemic in each city make them good candidates for conducting an RCT among YMSM. These cities represent distinct geographical regions (i.e. Midwest, Southeast, East Coast) with notable differences in population demographics and culture. This diversity will allow examination of whether the intervention works equally well in a variety of urban settings, thus increasing our ability to draw conclusions about the generalizability of findings. Given site-specific recruitment patterns, we will readily achieve representation across White, Black, and Latino groups, but we will also stratify enrollment to equal 1/3 for each group). Each site will screen approximately 1250 YMSM and enroll approximately 250 YMSM.

Inclusion and exclusion criteria: We will include participants in the study if they: (1) MSM, defined as a birth male who identifies as male and who self-reports having sexual contact with another male in the past year; (2) received an HIV negative test result from a participating clinic/recruitment site; (3) are 18-29 years old; and (4) had unprotected anal sex with another male in the last 6 months. YMSM will not be enrolled in the study if they: (1) do not have an e-mail address that can be used to contact them for retention purposes; (2) are currently in a behaviorally monogamous relationship lasting longer than 6 months. We use this criterion because we believe safer sex interventions for MSM in long-term monogamous relationships will require substantial tailoring from those who are single or in the early phases of a relationship; (3) did not have unprotected anal sex with another male in the last 6 months. Consistent with recommendations for assuring sufficient event rates in RCTs , this will ensure that sufficient rates of sexual behavior are occurring at pre-test to allow us to detect intervention effects on behavior at follow-up; (4) HIV positive serostatus at time of enrollment. We have elected to exclude HIV+ individuals because we believe that secondary prevention messages may need to be different than primary prevention messages. Nevertheless, if a participant seroconverts during the course of the study, he will be allowed to continue participating (with appropriate adjustment in the analyses). We will also refer him for HIV services (see below); and (5) since the measures and intervention are delivered in English, participants must be able to read English at a minimum 8th grade level. Our developmental R34 KIU! data, and data on client flow at our recruitment sites, suggest that despite having many exclusion criteria we will be able to meet our target recruitment goals.

YMSM will participate in either usability and acceptability tests in phase 1 or the RCT in phase 2. In phase 1 (months 1-6), we will perform necessary technological upgrades to the tracking system, program additional booster modules, conduct usability testing, and prepare for the RCT. Twelve ethnically diverse YMSM (4 Caucasian, 4 African American, 4 Latino) will participate in usability and acceptability testing of new booster session and the existing modules that will be updated with video interviews conducted in New York and Atlanta. A testing protocol established by the Northwestern University Center for Behavioral Intervention Technologies (CBIT) will be used to assess usability across standards (i.e. across different monitors, bandwidths, etc.) and in practice with target participants who will "think out loud" and be observed as they go through the modules (i.e. ability to navigate, cultural appropriateness). Participants in usability testing will be reimbursed \$35 in cash for approximately 90 minutes of their time and for travel expenses.

In phase 2 (months 7 – 48), 4500 YMSM will participate in the RCT phase of the study. About 20% of these young men (n = 900) are anticipated to enroll into and complete the study. Participants will be automatically randomized into the experimental intervention (KIU!) or the control condition (HIV Knowledge) after verification of participant eligibility and completion of informed consent online. Randomization will be stratified by race and recruitment clinic. In both arms of the trial we will test for Gonorrhea (NG) and Chlamydia (CT), using the athome rectal swab test kits and at-home urine test kits, and refer for treatment as necessary at baseline and post-intervention. In the experimental condition, participants will have already received HIV testing and counseling, and in the context of the proposed study will receive the highly-interactive and YMSM-tailored Internet-based prevention program called Keep It Up! (KIU!). Consistent with meta-analytic data on effective HIV interventions, the content will be delivered over three sessions across a three week period (see Appendix

1 for intervention overview). Participants in the KIU! arm will also receive booster sessions at 3- and 6--months from completion of the intervention. These sessions continue to provide HIV prevention motivation and behavioral skills training.

In the control condition, participants will also have already received HIV testing and counseling. In the context of this study they will receive the HIV-information modules that focus on facts about HIV and STIs. There are similarly 7 modules in this informational curriculum that, just like the KIU! arm, must be completed across three sessions. YMSM in this control arm will receive booster sessions at 3- and 6-months that provide further facts about HIV and STIs.

We acknowledge the importance of considering the ethical ramifications of delivering an HIV information-only control condition to a group at high risk for HIV infection. Ethical objections to randomization with a control group generally center around situations where an existing effective intervention exists. In the case of online HIV prevention with YMSM no such proven-effective intervention exists. We highlight that in our pilot RCT the information control condition showed increased HIV knowledge as a product of their participation, and therefore the control group does receive a benefit from participation. We take the view that properly designed and conducted RCTs are ethical when they answer important public health questions without impairing the welfare of participants who provide informed consent.

Participants in both conditions will complete all assessment materials. Similar procedures and measures successfully used in the developmental R34 study will be employed. Assessments will be completed via the Internet using an Internet-based Computer-Assisted Self Interview (CASI). Assessments will occur at baseline, 3-,6-, and12-month post intervention. At each log-in to the intervention we will ask about the physical setting where the participant is located. We will assess levels of privacy, distractions, and the type of location. At each assessment point participants will be asked if they have experienced any adverse events as a result of their participation in the program. Endorsement of adverse events will trigger an email alert to the principal investigator who will respond expeditiously. Participants will also be given a contact number to call if they need more immediate assistance in regards to the adverse situation. Note that in the pilot trial no participants reported adverse events during the trial.

Each assessment will take less than 30 minutes. As we have done successfully in prior online studies, participants will be given the option of receiving payment in person or via mail. Payments will be made after each of the following tasks are completed:

- 1. Baseline payment will vary based on enrollment site.
  - a. For participants who enroll off-site (e.g. at home or at a library), a \$30 pre-loaded Citi VISA card will be given after participants complete the baseline assessment and the CDC lab receives the first STI test kit sample.
  - b. For participants who enroll on-site at Emory University, Hunter College, or Northwestern University, \$50 in cash will be given after participants complete the baseline assessment and STI testing. We will give these participants a consent form upon arrival describing the payment they will receive for completing the baseline assessment and STI testing on-site a university site.. University staff will mail the STI test samples to the CDC.
  - c. For participants who enroll on-site at a CDPH clinic, \$50 in cash will be given after participants complete the baseline assessment and STI testing (or consent to the clinic's UIC lab sharing their STI results). We will give these participants a paper consent form upon arrival describing the payment they receive for completing the baseline assessment and STI testing on-site at a CDPH clinic.
- 2. \$20 pre-loaded Citi VISA card will be given after participants complete last intervention module and post-intervention assessment.
- 3. \$20 or \$30 pre-loaded Citi VISA card will be given after the participant completes the 3-month booster session and assessment. Participants who only complete the 3 month booster session and assessment will receive a \$20 pre-loaded Citi VISA card. Participants who take at-home STI tests, in addition to completing the 3 month booster session and assessment, will receive a \$30 pre-loaded Citi VISA card.

- 4. \$20 or \$30 pre-loaded Citi VISA card will be given after the participant completes the 6-month booster session and assessment. Participants who only complete the 6 month booster session and assessment will receive a \$20 pre-loaded Citi VISA card. Participants who take at-home STI tests, in addition to completing the 6 month booster session and assessment, will receive a \$30 pre-loaded Citi VISA card.
- 5. \$30 or \$50 pre-loaded Citi VISA card will be given after participants complete the 12-month assessment and the CDC lab receives the second STI test kit sample. The standard payment for this follow-up is a \$30 pre-loaded Citi Visa card. Participants who are difficult to reach and are out of window for completing their final assessment and STI test kit will be offered a \$50 pre-loaded Citi Visa card. These participants typically do not respond to contact attempts and do not complete one or more assessments. Non-responsive participants and those who did not complete previous assessments will also be offered a free movie ticket to AMC Theaters. Increased incentives like this have been shown to increase participation and retention among hard to reach and non-responsive participants in other research studies without perceptions of coercion. Younger participants (18 24 years old) also make up a larger portion of participants who are hard to reach or non-responsive. Latino and African American YMSM make up more than 60% of participants who are hard to reach or non-responsive. As these groups are most at risk for HIV, it is very importance to collect outcome data from them as a means of seeing how useful the intervention is in reducing risks among groups that are most in need of effective HIV prevention interventions.

Participants who come on-site to Emory, Hunter, or Northwestern to complete an assessment and/or STI testing will be given the option to receive payment in cash.

There are six different total amounts of incentives that a participant can receive. The different amounts are determined by enrollment site and STI status at baseline. Across all possible combinations of enrollment site and STI status, the maximum payment amount is \$160 for participants who enroll on-site and test positive for STIs at baseline. See the table below for a detailed description of the six tier incentive structure:

|    |   | Payment Schedule |              |                      |                      |                       |       |
|----|---|------------------|--------------|----------------------|----------------------|-----------------------|-------|
|    |   | Baseline         | Intervention | 3 Month
Follow-up | 6 Month
Follow-up | 12 Month
Follow-up | Total |
| Pa | rticipants who  |                  |              |                      |                      |                       |       |
| _  | Enroll on-site Test positive for STIs at baseline and repeat testing at all follow-ups  | \$50             | \$20         | \$30                 | \$30                 | \$30                  | \$160 |
| _  | Enroll on-site Test negative for STIs at baseline and repeat testing at 12 month follow-up            | \$50             | \$20         | \$20                 | \$20                 | \$30                  | \$140 |
| _  | Enroll off-site Test positive for STIs at baseline and repeat testing at all follow-ups | \$30             | \$20         | \$30                 | \$30                 | \$30                  | \$140 |
| _  | Enroll off-site Test negative for STIs at baseline and repeat testing at 12 month follow-up           | \$30             | \$20         | \$20                 | \$20                 | \$30                  | \$120 |

Study Title: Efficacy of Internet-based HIV Prevention (PI: [name]); Research Protocol STU00073433, Version Date: 12/12/16; Page 28 of 50

IRB #: STU00073433 Approved by NU IRB for use on or after 8/22/2017 through 8/21/2018.

| _ | Enrolled on-site         |      |   |   |   |      |                  |
|---|--------------------------|------|---|---|---|------|------------------|
| - | One or more incomplete   |      |   |   |   |      | \$100 -          |
|   | assessments              | \$50 | - | - | - | \$50 | \$180 -
\$180 |
| - | Completes 12 month       |      |   |   |   |      | \$100            |
|   | assessment and test kit  |      |   |   |   |      |                  |
| _ | Enrolled off-site |      |   |   |   |      |                  |
| - | One or more incomplete   |      |   |   |   |      | \$80 -           |
|   | assessments              | \$30 | - | - | - | \$50 | \$160            |
| - | Completes 12 month       |      |   |   |   |      | \$100            |
|   | assessment and test kit  |      |   |   |   |      |                  |

In our online and telephone recruitment ads, as well as the print ads that are displayed at our CBO partner sites, we will advertise the \$120 incentive. We anticipate that most participants will enroll off-site and only complete STI testing at baseline and 12-month follow-up. At our university sites and CDPH sites where participants are able to enroll by completing the baseline assessment and STI testing, we will post print ads that advertise the \$140 incentive. We also anticipate that most of these participants will only complete STI testing at baseline and 12-month follow-up.

We will randomly select 20 participants to complete a short phone exit interview after their 12 month follow-up assessment. Participants will be compensated with a \$5 gift card as thanks for their time and participation.

We will also randomly select 20 participants who tested positive for rectal STIs more than once during the study to complete a brief phone interview focused on their experiences getting tested for and seeking treatment for rectal STIs. Participants will be compensated with a \$10 gift card as thanks for their time and participation. Participants who are difficult to reach (defined as non-responsive to 3 contact attempts) will be offered a \$20 gift card as thanks for their time and participation.

We will maintain up-to-date contact information by contacting each participant monthly using their preferred mode of communication. E-raffles will take place at monthly intervals. Participants will be sent an e-mail that includes a link, that when clicked enters them in a raffle to win a \$50 pre-loaded Citi VISA card. Based on projected recruitment of 264 participants per year, we estimate the odds of winning a raffle are 1 in 264 (or 3.78%). Participants will be entered in 11 raffles during their study enrollment.

